### **5.9. Time to First Event**

First of any component event (cardiovascular death, hospitalization for heart failure, cardiac assist device, and heart transplant) will be evaluated descriptively with Kaplan-Meier time-to-event methods. The event date will be the date of the first component event. Subjects without a component event will be censored at the date of last contact. The estimate of event free survival and corresponding 95% log-log confidence interval as well as the number of subjects at risk and number of subjects with an event will be presented at 6 months, 12 months, 24 months, and annually thereafter. The hazard ratio between arms and its 95% confidence interval will be estimated by a proportional hazard's regression model. Time to first event analyses will be repeated for each event type individually (separate analyses for cardiovascular death, hospitalization for heart failure, cardiac assist device, and heart transplant).

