## 3. PRIMARY AND FOCUSED ENDPOINTS

### 3.1. Primary Endpoint: Rate of CV Mortality and HF Morbidity

#### 3.1.1. Rate of Cardiovascular Mortality and Heart Failure Morbidity

The objective is to demonstrate that treatment with the BAROSTIM NEO System, relative to medical management, reduces the rate of cardiovascular mortality or worsening heart failure that leads to hospitalization or emergency room visit, cardiac assist device or heart transplant.

Subjects will be censored at the time of a terminal event (i.e., death, permanent cardiac assist device, heart transplant, or novel implantation of a device to receive Cardiac Contractility Modulation) or end of follow-up, whichever occurs first.

The end of follow-up for analysis of morbidity and mortality will occur on the last date where adverse event status is known for the subject. This definition of follow-up time ensures that only time periods where morbidity and mortality status has

been assessed are included. End of follow-up is defined for each subject as the later date of:

- Last study visit
- Last date of adverse events reported in the database:
  - If last adverse event is a hospitalization, use discharge date
  - If last event is not a hospitalization, use resolution date if resolved, else use onset date
- Date subject completed the final, protocol defined end of study visit (note: this only occurs at end of study)

This end of follow-up date will be used to calculate follow-up time for the negative binomial model.

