## 5. SUPPORTING MORBIDITY AND MORTALITY ANALYSES

These endpoints will provide additional supporting analyses to aid interpretation of the morbidity and mortality data. These analyses may include events included in the heart failure expanded definition and/or heart failure equivalent events, as defined in Section 2, as appropriate for the endpoint.

The analyses of the focused endpoints will be based on descriptive statistics, nominal two-sided 95% confidence intervals and p-values. No statistical adjustment for multiple comparisons will be made.

These analyses are intended to support any updated labeling for patients with heart failure.

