### 5.1. Cardiovascular Mortality and Heart Failure Morbidity N

These two endpoints are similar to the primary and first focused endpoint, except they also include the following hospitalization equivalent events: Hospital-based observation unit and unscheduled clinic visits.

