#### 5.1.1. Rate of CV Mortality and HF Hospitalization / Hospitalization Equivalent

The objective is to demonstrate that treatment with the BAROSTIM NEO System, relative to medical management, reduces the rate of cardiovascular mortality or worsening heart failure that leads to any of the following events:

- Hospitalization for heart failure OR
- Emergency room visit for heart failure OR
- Hospital-based observation unit for heart failure OR
- Unscheduled clinic visit for heart failure OR
- Cardiac assist device OR
- Heart transplant

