#### 5.4. Reduction of the Components of the Endpoint

The objective is to demonstrate that treatment with the BAROSTIM NEO System, relative to medical management:

- Reduces the rate of hospitalizations for heart failure\*
- Reduces the rate of hospitalizations for heart failure\* or emergency room visits for heart failure
- Reduces cardiovascular mortality
- Reduces LVAD or heart transplant
- Reduces LVAD
- Reduces heart transplant
- Reduces cardiovascular mortality, LVAD or heart transplant

\*May include hospitalization equivalent events, as well as heart failure events using the expanded definition.

For the analyses that include hospitalizations and hospitalization equivalent events only, the primary analysis will be a semi-parametric frailty model (as described in Section 4.2) that adjusts for the competing risk of the censoring events (e.g., cardiovascular mortality and/or LVAD and/or heart transplant).

For the analyses that include censoring events only, the analyses will be evaluated descriptively with Kaplan-Meier time-to-event methods. The event date will be the date of censoring event. Living subjects will be censored at the date of last contact. Subjects that die due to non-cardiovascular causes will be censored at the date of death. The estimate of survival and corresponding 95% log-log confidence interval as well as the number of subjects at risk and number of subjects that die will be presented at 6 months, 12 months, 24 months, and annually thereafter. The hazard ratio between arms and its 95% confidence interval will be estimated by a proportional hazard's regression model.

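### SAP 5.9 claims to analyse the first of any component event, but neither of its lists names the heart failure emergency room visit that belongs to the primary composite

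*SAP*

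**What the plan says.** SAP 3.1.1 sets the primary endpoint as the rate of cardiovascular mortality or "worsening heart failure that leads to hospitalization or emergency room visit, cardiac assist device or heart transplant". Protocol 4.3.1 defines it in the same terms.

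SAP 5.9 adds a supporting analysis of "First of any component event (cardiovascular death, hospitalization for heart failure, cardiac assist device, and heart transplant". It is to be "evaluated descriptively with Kaplan-Meier time-to-event methods", with a hazard ratio from a proportional hazards model. Subjects without a component event are censored at last contact. The section closes by repeating the analysis for each event type: "separate analyses for cardiovascular death, hospitalization for heart failure, cardiac assist device, and heart transplant". The ER visit is in neither list.

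Elsewhere the SAP names ER visits separately. SAP 5.1.1 gives them their own line ("Emergency room visit for heart failure OR"). SAP 5.4 has one item for HF hospitalizations and a second that adds "or emergency room visits for heart failure".

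**The concern.** The section announces every component and then names all but one. A programmer who builds the event flag from the list in 5.9 would leave out an HF ER visit that did not end in admission, although the same visit counts in the primary analysis.

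The introduction to SAP Section 5 says these analyses are there to help interpret the morbidity and mortality data and to support updated labeling. Readers will set the 5.9 curve and hazard ratio beside the primary rate ratio. Those two already differ because one uses first events and the other uses all events. If the component set differs as well, a discrepancy has two possible sources, and nothing in 5.9 tells the reader that the second one exists.

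**Working it through.** No formula applies. SAP 5.9 states no sample size, event count, power or alpha, so the check is a comparison of texts.

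**Step 1. Component lists side by side.**

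| Event type | Primary composite (Protocol 4.3.1, SAP 3.1.1) | SAP 5.9, composite | SAP 5.9, repeats by type |
|---|---|---|---|
| Cardiovascular death | yes | yes | yes |
| HF hospitalization | yes | yes | yes |
| HF ER visit | yes | not named | not named |
| Cardiac assist device | yes | yes | yes |
| Heart transplant | yes | yes | yes |

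Five types stand in the primary composite and four in 5.9. The omission occurs twice, so it does not look like a slip in a single list.

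**Step 2. Does the SAP use hospitalization to include ER visits?** In several places it keeps them apart:
- SAP 5.1.1 lists them as separate events.
- SAP 5.4 analyses hospitalizations with and without ER visits. That distinction would be empty if one term contained the other.
- SAP 3.2.1 attaches the expanded definition to hospitalization and to ER visit separately.
- SAP 3.2.2 names emergency department visits next to hospitalizations in its third tier.
- The endpoint closing date in SAP Section 2 refers to both hospital and ER admissions.

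**Step 3. Does another sentence bring ER visits into 5.9?** The introduction to Section 5 says its analyses "may include events included in the heart failure expanded definition and/or heart failure equivalent events". SAP 5.1 says what the equivalents are: "they also include the following hospitalization equivalent events: Hospital-based observation unit and unscheduled clinic visits". ER visits are not among them. The expanded definition relaxes documentation requirements and does not itself add an event type to the 5.9 list. Neither route closes the gap.

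**Step 4. What a literal reading does to a subject's data.** Let t1 be the time of an HF ER visit without admission and t2 the time of a later listed event.
- The ER visit is the first primary event and a listed event follows: 5.9 dates the subject at t2 instead of t1, so event-free time is too long by t2 − t1.
- The ER visit is the only primary event: 5.9 censors the subject at last contact as event-free.
- The ER visit leads to admission: it would normally be captured as a hospitalization, with little or no difference.
- A listed event comes before the ER visit: the first-event analysis does not change.

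Only the first two patterns matter. Under them, the event-free probability being estimated is at least as high in each arm as for the primary composite. The hazard ratio could move either way, depending on how such visits divide between the arms.

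**Step 5. Size.** Neither document gives the number or share of ER-only events, overall or as first events. The shift in the curve or the hazard ratio cannot be computed.

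**The case against.** The strongest reply is that the four items are the documents' usual shorthand and that hospitalization already covers the ER visit.
- Protocol 4.3.1 refers the reader to 4.3.4 for the component definitions, and 4.3.4 defines exactly the four types in SAP 5.9.
- Protocol 3.4.5 gives much the same four when it tells sites which endpoint events to collect after partial withdrawal.
- The rationale in SAP 3.2.1 speaks of ER visits that the CEC judges to be heart failure hospitalizations.
- SAP 5.3 describes the primary effect as made up of censoring events and recurrent HF hospitalizations.
- The note to inclusion criterion 4 lets an ER visit count as an HF hospitalization, though only for eligibility.
- The CEC Charter governs event definitions and supersedes the protocol. If it takes the broad view, 5.9 already includes ER visits.

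This stands as a reason for doubt. A reader might infer that 5.9 certainly does not analyse the primary composite. The documents do not establish that, because the Charter is not among them. But the separate listings in SAP 5.1.1 and 5.4 mean the broad reading cannot be assumed either.

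The reply also holds on consequences. A reader might infer that a disagreement between 5.9 and the primary could not be interpreted. That goes too far: first-event and recurrent-event estimates can differ even with identical components. SAP 5.3 also applies Andersen-Gill and joint frailty models to the endpoints, and 5.4 shows hospitalizations with and without ER visits. A mismatch in components makes the comparison harder, no more.

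A reader might also suppose that the gap matters most after March 2020. SAP Section 7 describes patients avoiding both emergency departments and hospitals, and remote care taking their place. It does not describe a shift from admission to ER visits.

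**Conclusion.** The inconsistency is real on the text. SAP 5.9 claims all components and twice omits one that SAP 3.1.1 and Protocol 4.3.1 include. Taken literally, its curve and hazard ratio describe a narrower composite than the primary, and only subjects whose first primary event is an ER visit without admission are affected.

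This rests on reading hospitalization in 5.9 as 5.1.1 and 5.4 use it. If the Charter classes HF ER visits as HF hospitalizations, only the wording is at fault. Any percentage of misdated subjects would be pure assumption.

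The importance is low. The analysis is supporting and descriptive with nominal inference, and the primary negative binomial test, its boundaries, type I error and power are untouched. It is still worth correcting, because the analysis is meant to support labeling and the correction costs almost nothing.

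**What to change.** Before unblinding, so that results cannot influence the choice of components:

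1. Add *emergency room visit for heart failure* to the composite list in SAP 5.9, so that it matches 3.1.1.
2. Make the repeats by event type consistent with it, for example by using *hospitalization or emergency room visit for heart failure* as one type, in line with the second item of 5.4. A stand-alone ER analysis is optional.
3. If the Charter already counts HF ER visits as HF hospitalizations, say so in 5.9. If they are left out on purpose, say that instead and stop describing the analysis as covering any component.

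The cost is a line or two in the SAP and a matching change to the event flag. HF ER visits are already adjudicated for the primary endpoint, so no new data are needed.

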#### 3.1.4. Analysis Method

The hypothesis test will be based on a Z-statistic for the estimate of  $\beta_1$  from a negative binomial regression model. Although randomization is expected to result in balanced baseline covariates between the two arms, the model will include the baseline covariate of number of heart failure hospitalizations 12 months prior to enrollment to adjust for any potential imbalances between the two arms. In SAS (version 9.4 code) this model is fit as follows:

```
proc genmod;  
  model nev=trt hfh / dist=negbin offset=lfutime;  
run;
```

where nev is the number of events, trt is an indicator variable of randomization to the treatment arm, hfh is the number of heart failure hospitalizations within the 12 months prior to enrollment, and lfutime is the logarithm of the follow-up time. The Z-statistic (Z) is the parameter estimate for trt divided by the associated standard error. A Wald test one-sided nominal p-value is calculated by calculating the standard normal tail probability  $\Phi(Z)$ . This simplified model has previously been demonstrated to provide treatment effect estimates in strict agreement with those obtained with the more complex joint model defined in the BADR.

Success for demonstrating a reduction in morbidity and mortality is determined by the z-statistic crossing the group sequential boundary at one of the pre-specified analyses whose timing is determined by reaching pre-specified numbers of events.

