### **5.10. Reduction of All-Cause Mortality**

All-cause mortality will be evaluated descriptively with Kaplan-Meier time-to-event methods. The event date will be the date of death. Living subjects will be censored at the date of last contact. The estimate of survival and corresponding 95% log-log confidence interval as well as the number of subjects at risk and number of subjects that die will be presented at 6 months, 12 months, 24 months, and annually thereafter. The hazard ratio between arms and its 95% confidence interval will be estimated by a proportional hazard's regression model.

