## 8. ASSUMPTIONS FOR THE PRIMARY MORBIDITY AND MORTALITY ENDPOINT

### 8.1. Power and Type I Error Calculation

Since a subgroup of patients with partial data has been previously analyzed, the relevant power and type I error for the future interim analyses is the conditional power and type I error, accounting for the fact that partial data has been previously analyzed. That previous analysis did not incur any alpha spending since there were no criteria for stopping the trial for success based on that analysis.

The conditional power and type I error are calculated by Monte Carlo methods using simulations of hypothetical trial data simulated according to the joint negative binomial model with parameters estimated based on the trial data through 03October2018.

Prospective follow-up and events from 03OCT2018 through trial completion at 320 events are simulated using a negative binomial model. Multiple hypothetical sets of future events are simulated and the pooled data, including observed and simulated data, is analyzed using the joint negative binomial model.

Pooling the data is equivalent to 100% borrowing. Pooling is performed in order to maintain the interpretability of the analysis, due to the intractability of separating the cumulative follow-up data into separate time periods while maintaining interpretability. The impact of 100% borrowing on type 1 error is accounted for by using a sufficiently rigorous nominal alpha such that conditional type 1 error is well controlled at less than 5%.

Programs will be provided to FDA that implement the Monte Carlo calculations.

Using 20,000 simulations for the null and 1000 simulations for the alternative under the assumptions below, the conditional power is 86.0% and the type I error is 4.4% when using an alpha spending function with a cumulative alpha level of 0.01. The stricter alpha level is sufficient to offset the tendency of the interim data to inflate the type 1 error. Using a group sequential spending function with a cumulative alpha of 0.01 results in controlling the type 1 error to less than 5% across a range of scenarios.

The base case uses the following assumptions for the conditional power and type I error calculations:

1. Control arm event rate of 0.4 events per patient year
2. Power calculated assuming an expected relative reduction in the endpoint event rate of  $1 - \exp(\beta_1) = 0.35$

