3. Type I error calculated assuming an expected relative reduction in the endpoint event rate of  $1 - \exp(\beta_1) = 0$ , equivalent to no treatment effect
4. Statistical significance threshold given by the Hwang-Shih-DeCani spending function with  $\gamma = -3$

5. Sample size of 331 subjects with baseline NT-proBNP < 1600, consisting of 259 subgroup subjects randomized through 03October2018 and an additional 72 subjects to be prospectively randomized.
6. Parameter describing the relationship between events in the year prior to randomization and the expected rate of events during follow-up (beta) of 1.8
7. Parameter describing the probability that an event is a censoring event (p) of 0.18
8. Parameter describing the dispersion of the negative binomial data (alpha) of 1.7

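### The first-event and mortality Cox models name no covariate, so their hazard ratios carry any chance imbalance in prior heart failure hospitalizations that the primary model adjusts for

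*SAP*

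**What the plan says.** SAP 5.9 describes the first component event as an outcome that "will be evaluated descriptively with Kaplan-Meier time-to-event methods", and then adds: "The hazard ratio between arms and its 95% confidence interval will be estimated by a proportional hazard's regression model". The same hazard-ratio sentence appears in 5.4 (components that are censoring events) and 5.10, and 5.12 uses Cox regression for heart failure death. SAP 5.10 is also descriptive: "All-cause mortality will be evaluated descriptively with Kaplan-Meier time-to-event methods". None of the four sections lists a covariate.

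The primary analysis differs. In SAP 3.1.4, "the model will include the baseline covariate of number of heart failure hospitalizations 12 months prior to enrollment to adjust for any potential imbalances". The SAP also names covariates elsewhere when it wants them: the 12-month walk, quality-of-life and NT-proBNP models in 3.2.4 list randomized group and baseline value.

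The introduction to Section 5 calls for "nominal two-sided 95% confidence intervals and p-values. No statistical adjustment for multiple comparisons will be made". That sentence speaks of the focused endpoints but stands in Section 5, and it is followed by: "These analyses are intended to support any updated labeling for patients with heart failure".

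Protocol 3.4.10 stratifies randomization by site only. SAP 4.2 accepts that the arms may be unbalanced within the NT-proBNP subgroup, because the subgroup was identified after those subjects were randomized. It plans a propensity-weighted analysis with history of heart failure hospitalization among the covariates. The introduction to Section 4 commits such sensitivity analyses for the primary endpoint and makes them optional for others.

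**The concern.** The plan's reason for adjusting the primary model applies equally to the Cox models. The subjects are the same, the randomization is the same, and the SAP's simulations treat prior-year events as a predictor of the follow-up rate. A Cox model with arm alone has two consequences.

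- Any realized imbalance in prior hospitalizations goes into the reported hazard ratio.
- The hazard ratio is non-collapsible, so leaving out a predictor of the outcome pulls the estimate toward 1.

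These hazard ratios will be read beside the adjusted primary rate ratio and may be used to support labeling. If the two disagree, covariate imbalance is one possible explanation that the plan could have removed in advance. Silence on covariates also leaves the choice open until after unblinding.

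**Working it through.** **The plan's own figures.** The SAP gives no power, event target or precision for these hazard ratios. Its nearest figure belongs to the primary test: "the conditional power is 86.0% and the type I error is 4.4% when using an alpha spending function with a cumulative alpha level of 0.01". That figure is conditional on arm-level data through 03OCT2018, which the documents do not report, so it cannot be reproduced and does not bear on the Cox models. What can be checked agrees: the alpha spent in Table 7 is 0.0019 + 0.0011 + 0.0024 + 0.0046 = 0.0100.

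**Inputs from the documents.**
- N = 319 (SAP 1); 1:1 allocation (Protocol 3.4.10); mean follow-up 2.3 years (Protocol 4.3.3).
- Control rate 0.4 per patient-year; rate ratio 1 - 0.35 = 0.65; terminal fraction 0.18 (SAP 8.1).
- Dispersion 1.7, used as a gamma shape because Table 4 labels 1.4 as large overdispersion.
- Two-sided 5% level (SAP 5).
- Prognostic strength: "Parameter describing the relationship between events in the year prior to randomization and the expected rate of events during follow-up (beta) of 1.8". The scale is not stated. It is either a rate ratio of 1.8 per prior event or a log coefficient, giving exp(1.8) = 6.05. A weaker value, 1.3, was added.

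**Assumptions not in the documents.** Prior hospitalizations 0/1/2 in 70/22/8% or 50/35/15% of subjects; uniform censoring around the 2.3-year mean.

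**Step 1: how large is a chance imbalance?** Ignoring site stratification, the SD of the between-arm difference in the share with a prior hospitalization is sqrt[p(1-p)(1/n1 + 1/n2)], with n1 = n2 = 159.5.
- p = 0.30: sqrt(0.21 x 2/159.5) = 0.051
- p = 0.50: sqrt(0.25 x 2/159.5) = 0.056

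A 10-point difference is therefore about 1.8 to 2.0 SD.

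**Step 2: Cox model with and without the count, first event** (3,000 simulated trials per row; each pair is arm only, then arm plus count):

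| Rate ratio per prior event | Share with prior | Events | Hazard ratio | SE of log HR | Power | Log HR shift per 10 points |
|---|---|---|---|---|---|---|
| 1.3 | 30% | 138 | 0.698, 0.696 | 0.173, 0.173 | 0.545, 0.550 | 0.028 |
| 1.3 | 50% | 138 | 0.694, 0.692 | 0.173, 0.173 | 0.560, 0.569 | 0.029 |
| 1.8 | 30% | 133 | 0.702, 0.693 | 0.176, 0.176 | 0.525, 0.554 | 0.065 |
| 1.8 | 50% | 133 | 0.707, 0.697 | 0.176, 0.177 | 0.510, 0.533 | 0.063 |
| 6.05 | 30% | 86 | 0.747, 0.690 | 0.219, 0.221 | 0.257, 0.390 | 0.201 |
| 6.05 | 50% | 92 | 0.753, 0.691 | 0.211, 0.213 | 0.268, 0.413 | 0.170 |

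On the hazard-ratio scale, a 10-point imbalance is a factor of exp(0.028) = 1.03 at 1.3, exp(0.065) = 1.07 at 1.8 and exp(0.201) = 1.22 at 6.05.

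The power gain comes from the estimate, not its precision. At 1.8 with 30%, the mean z goes from ln(0.702)/0.176 = -2.01 to ln(0.693)/0.176 = -2.08, with the same standard error.

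**Step 3: a second simulation under other assumptions.** Follow-up was 1.5-4.5 years and prior counts 0/1/2/3 in 55/30/10/5%, with 2,500 trials per setting. At 1.8, power goes from 0.56 to 0.60 and the hazard ratio from 0.71 to 0.70. The SD of the difference between the two log hazard ratios is 0.027 at 1.3 and 0.059 at 1.8.

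**Step 4: mortality, by assumption only.** Take the terminal-event rate 0.18 x 0.4 = 0.072 per year as a proxy for mortality, and suppose prior hospitalizations act on it as on the composite (1,500 trials per setting). At 1.8 there are about 38 events. A 10-point imbalance shifts the log hazard ratio by 0.07-0.08 (0.03 at 1.3; up to 0.24 at 6.05). Power at 1.8 hardly moves: 0.228 to 0.231, and 0.209 to 0.209.

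**The case against.** The case for leaving the plan alone is substantial.

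- **Descriptive status.** These analyses have no hypothesis or power target. Success rests on the primary model, which is already adjusted. This stands.
- **Arm-only is legitimate.** An arm-only hazard ratio is a valid marginal summary and matches the Kaplan-Meier curves beside it. Over repeated randomizations, chance imbalance is already part of the interval's sampling error. This stands, and it is why the arm-only figure should still be shown. It does not help a reader who faces one realized imbalance in a known predictor.
- **Size.** At 1.8, a 10-point imbalance moves the log hazard ratio by 0.065/0.176 = 0.37 of its standard error, and such an imbalance is uncommon. This stands.
- **SAP 4.2.** Its weighted analysis is worded per endpoint and includes history of heart failure hospitalization. That is partial cover: the Section 4 introduction makes it optional outside the primary endpoint, and it would be a separate estimate.
- **Silence.** The SAP never calls the Cox models unadjusted, and the main SAP that it supplements is not available here. Arm-only is the natural reading, because covariates are named elsewhere. If adjustment was intended, the covariate still needs to be stated.
- **Sparse components.** Transplant-only and assist-device-only models may have too few events for a second term. This stands and limits the fix.

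**Conclusion.** The point holds as a minor one. The Cox models in SAP 5.4, 5.9, 5.10 and 5.12 omit a covariate that the plan itself considers necessary in the primary model, with only optional cover from 4.2. For first event at a rate ratio of 1.8, a 10-point imbalance shifts the log hazard ratio by about 0.06-0.07, and average attenuation is about 0.01 on the hazard ratio. The nominal power gain is 2-4 points at 1.8 and under 1 point at 1.3. It reaches 13-15 points only if beta is a log coefficient, which the SAP neither states nor excludes. All of this depends on the assumed prior-hospitalization distributions.

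A reader might infer three stronger conclusions that the documents do not support.
- **Real power or precision is being lost.** No power is claimed for these analyses, and the standard error does not improve with the covariate.
- **Adjustment would make the hazard ratio comparable with the primary rate ratio.** With a simulated rate ratio of 0.65, the first-event hazard ratio is about 0.71 unadjusted and 0.70 adjusted. Most of the gap comes from analyzing first rather than recurrent events and from remaining between-subject variation.
- **The mortality hazard ratios are known to be distorted.** The documents link prior events only to the composite event rate, so the mortality figures rest on an assumption.

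**What to change.** Before unblinding, state the Cox covariates in these places: 5.9 for the first composite event and for heart failure hospitalization, 5.10, 5.12, and the cardiovascular-mortality analyses of 5.4 and 5.9. Fit randomized arm plus the same prior heart failure hospitalization count as in 3.1.4. Keep the Kaplan-Meier curves unadjusted and show the arm-only hazard ratio beside them. Leave the assist-device-only and transplant-only models arm-only if events are few, and say in advance how that will be decided. It would also help to state the scale of beta in 8.1.

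The cost is one covariate in the model statements and one extra hazard ratio per table. The count is already collected for the primary model, so no new data are needed and the primary test does not change.
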